Study Rationale	
Eosinophilic esophagitis (EoE) is a chronic, debilitating, allergic/immune-mediated disease due to chronic esophageal inflammation with the development of dysphagia that affects food intake and quality of life. The disease is characterized by symptoms related to esophageal dysfunction and by eosinophil-predominant inflammation of the esophageal mucosa. While eosinophils are present in specific regions of the gastrointestinal (GI) tract, they are not normally found in the esophagus. Patients with EoE demonstrate esophageal tissue infiltration of significant numbers of eosinophils and other pro-inflammatory cells characterized by an enrichment of CD4+ T regulatory and type 2 cytokine producing effector type 2 T helper (Th2) cells. This infiltrating cellular profile along with over expression of cytokines, particularly interleukin-13 (IL-13) and interleukin-5 (IL-5), strongly suggests that EoE is a type 2 cell-mediated inflammatory disease.
 
The treatment options for EoE include diet avoidance, and off-label use of topical steroids or proton pump inhibitors. Diet avoidance can be successful in eliminating symptoms and leading to normalization of the esophageal eosinophilia. However, six-food elimination diet which has success rate of 70% and elemental diet with a success rate of 90% have a tremendous amount of patient and family burden. Patients have a very restricted diet with increased costs to the family and reduced quality of life. The new biologics, in particular, dupilumab has shown to high rate of clinical and histologic remission in 2/3 of patients in treatment of EoE in adolescents and adults. Dupilumab is approved for the treatment of atopic dermatitis and asthma for children greater than or equal to 6 years of age.
 
The goal of this study is to show that foods can be safely added to diet when on dupilumab without exacerbation of Eosinophilic Esophagitis when on standard of care treatment for EoE.

Study Objective	To determine if dupilumab can allow EoE trigger foods without inducing flares of EoE (histological or symptomatic)

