In preliminary data for this study¹³, we performed a retrospective chart review of patients with EoE using dupilumab for approved indications (asthma or atopic dermatitis). We identified 45 patients age 6 to 19 years of age and we have follow-up data for 41 patients. 39/41 patients showed improvement in EoE symptoms and we have follow-up endoscopies in 26 endoscopies showing normalization of histology in 22 patients and maintenance of normal endoscopy and histology in one additional patient while stopping their other medications to treat their EoE. However, 80% of the patients were still on a combination of medications and diet to treat their EoE. This current study will examine if the use of dupilumab for the treatment of Eosinophilic Esophagitis will allow expansion of their diet. The goal of expansion of diet will improve quality of life, nutrition without negatively affecting their EoE. We will examine EoE using validated EoE measures for disease activity and nutrition status by weight (z-scores).

The validated measures for endpoints in Eosinophilic Esophagitis to be used include

- Pediatric Eosinophilic Esophagitis Symptom Score²¹
- EoE Endoscopy Reference Score²²
- EoE Quality of Life²³
- EoE Histology Scale²⁴
- Esophageal Compliance (Endoflip)²⁵
- Height and Weight, calculated z-scores

We would also examine if the use of dupilumab will normalize the esophageal transcriptome by examining esophageal biopsy mRNA transcriptome. In EoE, there is an altered esophageal transcriptome with an increase expression of specific esophageal and T2 cytokines.²⁶ Both T cell profile and peripheral blood eosinophilia and eosinophil progenitors have shown correlation with esophageal biopsy and maybe a non-invasive marker of disease.^{4, 27} We will examine these research bloods to explore potential non-invasive markers of disease and/or mechanism of dupilumab on disease activity.

The goal of this study is to see if dupilumab can facilitate food introduction while patients on standard of care EoE therapies. They will maintain their EoE therapies, which can include PPIs, swallowed steroids, or diet elimination. throughout the study except for food introduction as indicated by the protocol.

We are examining food introduction in this age group for the following reasons.

- 1) Dupilumab is approved for children 6 years and above for asthma and atopic dermatitis

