3.4.1 Inclusion Criteria

3.4.2 Index/Case Subject Inclusion Criteria

- 1) Males or females age 6 to 25 years
- 2) Diagnosis of Eosinophilic Esophagitis based on the most recent international consensus definition (Dellon et al, Gastroenterology 2019)
 - a) History of endoscopy with a peak count of >15 eosinophils per high powered field meeting consensus criteria for Eosinophilic Esophagitis¹
- 3) History of either milk, egg, soy, or wheat induced EoE based on the following criteria in the last two years
 - a) Addition of a single food lead to exacerbation of esophageal eosinophilia (increase of greater than 15 eos/hpf) or
 - b) Removal of a single food lead to normalization of biopsy (esophageal eosinophilia showed less than 6 eos/hpf)

AND

 - c) History of either milk, egg, soy, or wheat induced EoE based on introduction of the food and symptoms in the last 12 months
- 4) Weight \geq 10 kg
- 5) Ability to remain on stable dose of PPI therapy throughout the study
- 6) Women with child bearing potential must have a negative urine/serum pregnancy test.
- 7) Parental/guardian permission (informed consent) and if appropriate, child assent.

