4.1 Study Treatment Phase: EoE disease control

4.1.1 Visit 1

Visit 1: Baseline Visit, Study enrollment

- Informed consent obtained,
- Inclusion and exclusion criteria reviewed,
- Medical Records reviews
- Physical exam including vital signs with height and weight
- Eosinophilic Esophagitis Symptom Score-Pediatric Eosinophilic Esophagitis Symptom Score (PEESS and PESQ)
- EoE Quality of life (QOL)
- Research labs (T cell phenotype, PBMC RNAseq, peripheral blood eosinophils and progenitors, proteomics)-15 ml
- First dose of Dupilumab

4.1.2 Visit 2

2 weeks from visit 1 (+/- 3 days)

- EoE Symptom Score-PEESS and PESQ
- Drug disposition
- Monitor drug compliance
- AE assessment
- Physical Examination including vital signs with height and weight

4.1.3 Visit 3

5 weeks from visit 2 (+/- 4 days)

- EoE Symptom Score-PEESS and PESQ
- Drug disposition
- Monitor drug compliance
- AE assessment
- Physical Examination including vital signs with height and weight

4.1.4 Visit 4

4 weeks from visit 3 (+/- 4 days)

- Upper Endoscopy with biopsy with 4 esophageal biopsies for histology
- EoE Symptom Score-PEESS and PESQ
- EoE QOL
- Drug disposition
- Monitor drug compliance

- AE assessment
- Physical Examination including vital signs with height and weight
- Endoflip and/or esophageal impedance
- Research bloods (T cell phenotype, PBMC RNAseq, peripheral blood eosinophils and progenitors, proteomics)-15 ml of blood
- Research Biopsies (esophageal RNAseq)-6 esophageal biopsies for research samples

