5.4.3.6 Eosinophilic Esophagitis Symptom Score

Improvement in symptom scores will be defined as a decrease in total symptom scores of two or

more from baseline to end of treatment. Subjects will be categorized based on whether they improved their symptoms. Subjects who improved their symptom scores were considered as responders and patients who did not improve their symptom scores were considered as non-responders.

The responses will be divided into three categories as suggested: Poor <30% improvement, good 30-70% improvement and excellent >70% improvement from baseline.

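### The exploratory symptom responder rule in Section 5.4.3.6 measures improvement since baseline, not freedom from symptomatic flare on trigger foods, and leaves low baseline scores unhandled

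*Combined protocol and SAP*

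**What the plan says.** All references are to the combined protocol and SAP.

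- **Responder rule, Section 5.4.3.6.** "Improvement in symptom scores will be defined as a decrease in total symptom scores of two or" more, from baseline to end of treatment. For everyone else, "patients who did not improve their symptom scores were considered as non-responders". There is no exception for a low or stable score.
- **Percent grades, same section.** "Poor <30% improvement, good 30-70% improvement and excellent >70% improvement from baseline". The section does not say which rule governs, whether the grades apply only to responders, or what to do when the baseline is 0.
- **Instrument, Section 4.1.1.** The Visit 1 list reads "Eosinophilic Esophagitis Symptom Score-Pediatric Eosinophilic Esophagitis Symptom Score (PEESS and PESQ"). Two instruments are collected. Section 5.4.3.6 does not say which one supplies the total score, and no score range is given.
- **Baseline.** Section 4.1.1 is titled "Visit 1: Baseline Visit, Study enrollment", which falls before the first dose. Section 3.1.1 also uses the word baseline for the week 12 endoscopy, after 12 weeks of drug.
- **Objective, protocol synopsis.** "To determine if dupilumab can allow EoE trigger foods without inducing flares of EoE (histological or symptomatic").
- **Entry, Section 3.4.2.** The symptom criterion is historical: "History of either milk, egg, soy, or wheat induced EoE based on introduction of the food and symptoms in the last 12 months". Sections 3.4.2 and 3.4.3 set no minimum current score. Section 1.5 says of background treatment: "They will maintain their EoE therapies, which can include PPIs, swallowed steroids, or diet elimination".
- **Other symptom analyses.** Section 5.3.2 lists change in score from baseline to end of treatment. Sections 5.4.3.2 to 5.4.3.4 add summaries by time point, paired tests against baseline, and a GEE model with baseline as the reference. Section 5.5 makes all non-primary testing exploratory.

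**The concern.** The trial asks whether subjects brought under control on dupilumab stay well once a trigger food returns. That is a question about maintenance, and the relevant comparison starts at the last visit before food. The responder rule asks about improvement, and under the Visit 1 reading it starts before drug.

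Two errors of interpretation follow. A subject who gains from the drug and then loses part of that gain on food can be reported as a symptom success. A subject who starts with few symptoms and keeps few symptoms on the food, which is the result hoped for, is reported with the same label as one whose symptoms flare. A published responder percentage built this way could mislead in either direction about food tolerance.

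Entry without a current-symptom threshold, on continued diet or drug therapy, makes low Visit 1 scores plausible, so the second problem is not remote.

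**Working it through.** The plan gives no figure for this rule, so there is nothing to reproduce. The check applies the rule to example scores. All scores are invented. A floor of 0 and whole-point steps are assumed.

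**1. Does the label track flare on food?** Fall = Visit 1 score minus week 51 score; responder if the fall is at least 2. Percent improvement = fall / Visit 1 score. Change on food = week 51 score minus week 12 score.

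| Visit 1 | Week 12 | Week 51 | Fall | Label | Percent grade | Change on food |
|---|---|---|---|---|---|---|
| 20 | 8 | 16 | 20 − 16 = 4 | responder | 4/20 = 20%, Poor | +8, doubled |
| 3 | 3 | 3 | 0 | non-responder | 0%, Poor | 0, stable |
| 3 | 3 | 6 | −3 | non-responder | below 0%, Poor | +3, doubled |

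The first subject doubled on food and is a responder. The second stayed well and shares both labels with the third, who doubled.

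Reading baseline as week 12 removes the first error (8 − 16 = −8, non-responder) but not the second. A subject stable at 8 has a fall of 0 and is also a non-responder. Low baselines also become more likely, because subjects have by then responded to drug.

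**2. Floor.** The largest possible fall from baseline B is B − 0 = B. For B = 0 or 1 this is below 2, so response is impossible. At B = 0 the percent change divides by zero.

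The share of subjects with a baseline below 2 is not in the documents. The ceiling on the responder rate is (N − k)/N, where k is the number with a baseline below 2:

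| Assumed share | k of 30 enrolled | Ceiling | k of 19 evaluable (Section 5.6) | Ceiling |
|---|---|---|---|---|
| 10% | 3 | 90% | 2 | 89% |
| 20% | 6 | 80% | 4 | 79% |
| 30% | 9 | 70% | 6 | 68% |
| 40% | 12 | 60% | 8 | 58% |

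**3. The two rules side by side.** A 2-point fall is graded Poor when 2/B < 0.30, that is, when B > 2/0.30 = 6.67.

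- 10 to 8: responder, 2/10 = 20%, Poor.
- 7 to 5: responder, 2/7 = 28.6%, Poor.
- 3 to 2: non-responder, 1/3 = 33%, Good.
- 1 to 0: non-responder, 1/1 = 100%, Excellent.

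The last two cases disappear if the grades apply to responders only. The first two remain either way.

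**The case against.** **The plan has other symptom analyses.** A reader might infer that a flare on food would go unseen. The documents do not support that. The listed secondary endpoint is the continuous change in score, summaries are given by time point with individual listings, and each time point is tested against baseline, so rising scores would be visible. What is missing is narrower: no contrast from the last pre-food visit is specified, and no proportion with or without worsening. The paired tests and the GEE use the same baseline as the responder rule.

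**Zero-score subjects may never reach food.** The synopsis (Study Phases) makes food introduction conditional on decreased symptoms, and Section 3.1 on histologic and symptom control. A score of 0 cannot decrease, so under the synopsis such a subject would not advance. Section 3.1.1 advances subjects on the eosinophil count alone. These passages disagree and must be reconciled. Until then it cannot be said that symptom-free subjects on trigger food will be counted as failures. The intent-to-treat population in Section 5.4.1 includes everyone enrolled, however, so a baseline of 0 or 1 would still enter the responder denominator.

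**A yes/no threshold and a percent grade can coexist.** This is fair. A reader might infer that the two rules contradict each other outright. A responder graded Poor is awkward but not contradictory, and the opposite-looking labels depend on grading non-responders too. What stands is that the link is not stated.

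**The consequence is limited.** This also stands. No treatment or diet decision in the documents uses the 2-point label.

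**Conclusion.** The concern holds in a limited form. The responder rule does not measure the objective it would be read against: it cannot separate staying well from flaring, and with Visit 1 as baseline it can call a flare on food a response. This follows from the wording and needs no assumption beyond which visit is the baseline.

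The floor problem is conditional. It rests on a scale that stops at 0, which the documents do not state, and its size cannot be derived. The ceilings of 90% to 60% on 30 subjects illustrate assumed shares and do not estimate the actual one.

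It would be wrong to infer that the trial's main result is at risk. The primary endpoint is histologic and takes all of the 0.05 alpha (Section 5.5). What is affected is an exploratory symptom summary in an open-label pilot. The change is still worth making, because that summary bears on half of the stated objective and the data to do it properly are already scheduled.

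**What to change.** Revise Section 5.4.3.6 as follows.

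1. Name the instrument that supplies the total score (PEESS or PESQ), and name the baseline visit.
2. Add the change in total score from the last pre-food visit to weeks 25 and 51, with 95% confidence intervals. The last pre-food visit is week 12, or later for subjects given 12 extra weeks of drug under Section 3.1.1; state which post-food visits apply to those subjects.
3. Add the proportion of subjects without worsening of 2 or more points over the same intervals, labelled exploratory. The threshold mirrors the plan's own 2-point rule; the documents offer no separate basis for it.
4. Limit the responder proportion to subjects with a baseline of at least 2, and report the others separately as remained low or worsened.
5. Show the percent grades descriptively, for non-zero baselines only, and say whether they apply to all subjects or to responders.

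The cost is SAP wording and a little more analysis. Table 1 schedules symptom scores at Visits 1 to 16, including weeks 12, 25 and 51, so no new data are needed. The downside is a smaller responder denominator.

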5.4.3.7 Vital Signs

The analysis of vital signs will focus on the incidence of clinically relevant abnormalities.

5.4.4 Pharmacokinetic Analysis

Not applicable, no pharmacokinetic assessments will be performed during this study.

5.4.5 Safety Analysis

All AEs will be coded by system organ class and preferred term using MedDRA.

Treatment-emergent AEs (TEAEs) will be defined as any AEs, regardless of relationship to study drug, which occur during AE collection period of study drug or any event already present that worsens in either intensity or relationship to study drug following exposure to the dupilumab. If relationship information is missing, the TEAE will be considered drug related.

An overall summary of TEAEs will be provided showing the number and percentage of subjects in each treatment group with any TEAE, any potentially drug related TEAE, any severe TEAE, any serious TEAE, any TEAE leading to discontinuation, and any TEAE leading to death. The number of events will also be presented.

The number of AEs as well as the number and percentage of subjects who experienced at least one AE will be summarized by system organ class, preferred term, and time period. The incidence of the following events will be summarized:

- TEAEs: incidence, severity, and duration.
- Potentially drug related TEAEs
- Discontinuations due to TEAEs
- Physical examinations, and vital signs
- SAEs
- Potentially drug-related SAEs

In addition, TEAEs will be summarized by relationship to study drug and by severity. If a subject has more than one occurrence of the same TEAE with different severities or relationship to study drug, then the TEAE will be assigned to the highest severity category and/or most related relationship category. If the intensity or relationship is missing, then the 'worst case' will be assumed (i.e., severe for intensity and drug-related for relationship).

Time period of an AE will be determined based on the start time of the AE.

5.5 Significance level and alpha allocation

The significance level for all statistical testing in this study will be 0.05, and the alpha of 0.05 will all be allocated entirely to the primary efficacy endpoint. All other statistical testing will be considered exploratory.

5.6 Sample Size and Power

In the phase 2 clinical trial, 67% of the active treated with dupilumab had less 6 eosinophils per high power field compared to zero in the placebo group.¹¹ In phase 3 trial, 59.5% of the dupilumab had less 6 eos/hpf and only 5% of the placebo treated group had less than 6 eos/hpf.^{36, 37}

Therefore, we would assume 64% efficacy rate (average between the 2 studies) from the initial enrollment allowing 19 evaluable subjects. A sample size of 20 with alpha of 0.05 and power 80% would allow detection of difference in eosinophil count of 11 (effect size of 0.7 based on 15 eosinophils/high power field being abnormal).

5.7 Interim Analysis

No interim analysis is planned.

6 STUDY MEDICATION (STUDY DEVICE OR OTHER STUDY INTERVENTION)

6.1 Description

Dupilumab, an interleukin-4 receptor alpha antagonist, is a human monoclonal antibody of the IgG4 subclass that binds to the IL-4R α subunit and inhibits IL-4 and IL-13 signaling. Dupilumab has an approximate molecular weight of 147 kDa.

Dupilumab is produced by recombinant DNA technology in Chinese Hamster Ovary cell suspension culture.

DUPIXENT (dupilumab) Injection is supplied as a sterile, preservative-free, clear to slightly opalescent, colorless to pale yellow solution for subcutaneous injection. DUPIXENT is provided as either a single-dose pre-filled syringe with needle shield or a single dose pre-filled pen in a siliconized Type-1 clear glass syringe. The needle cap is not made with natural rubber latex. Available dupilumab dosing:

- Injection: 300 mg/2 mL solution in a single-dose pre-filled syringe with needle shield.
- Injection: 200 mg/1.14 mL solution in a single-dose pre-filled syringe with needle shield.
- Injection: 100 mg/0.67 mL solution in a single-dose pre-filled syringe with needle shield
- Injection: 300 mg/2 mL solution in a single-dose pre-filled pen.
- Injection: 200 mg/1.14 mL solution in a single-dose pre-filled pen.

Pre-filled pen will be used in adults and pediatric patients aged 12 and older and the pre-filled syringe will be used for adults and pediatrics patients aged 6 years and older.

6.1.1 Labeling

Description of product label

6.1.2 Dosing

Dosing will be done based on current doses in phase 3 clinical trials for EoE. The dose will not be adjusted based on changes in weight during the study protocol.

Dupilumab Dosing Scale: per the current Eosinophilic Esophagitis trials (R668-EE-1877 and R668-EE-1774) and approved dosage for 12 yo > 40 kg:

Weight		
≥ 12 years of age	> 40 kg	300 mg SQ weekly
	30-39.9 kg	300 mg SQ Q2W
	15-29.9 kg	200 mg SQ Q2W
6-11 years of age	10-14.9 kg	100 mg SQ Q2W
	> 15-29.9 kg	200 mg SQ Q2W
	$\geq 30-60$ kg	300 mg SQ Q2W
	≥ 60.1 kg	300 mg SQ Q2W

6.1.3 Treatment Compliance and Adherence

It is the Investigators' responsibility to ensure that subjects are correctly instructed on how to take their study medication. Records of study medication used and intervals between visits will be kept during the study. Subjects will be asked to return their unused medication (box(es)) when they come back for their study visits. All unused medication (boxes) should be returned at each study visit and the end of the study. The study drug will be dispensed by the Investigator, or by a qualified individual under the Investigator's supervision.

At each visit, prior to dispensing trial medication, previously dispensed trial medication will be retrieved by the Investigator and compliance assessed. A compliance of > 80% over the treatment period is sought. Subjects exhibiting poor compliance as assessed by counts and response to the question "Did you take your dupilumab regularly?" will be counseled on the importance of good compliance to the study dosing regimen.

Non-compliance is defined as taking less than 80% of trial medication during any evaluation period (visit to visit). Subjects who are persistently non-compliant may be withdrawn from the study.

6.1.4 Drug Accountability

All supplies of dupilumab will be accounted for in accordance with GCP. There will be an individual study drug accountability record for each subject and the Investigator will maintain accurate records of the disposition of all trial medication supplies received during the study. These records will include the amounts and dates that clinical drug supplies were received, dispensed to the subject, returned by the subject, and returned to the Investigator or destroyed on site. The unused dupilumab will be returned on subsequent study visits. The excessive and used study drug will be destroyed by The Children's Hospital of Philadelphia Research Pharmacy using standard protocols. The research pharmacist will provide a corresponding certificate of destruction.

7 SAFETY MANAGEMENT

7.1 Clinical Adverse Events

Clinical adverse events (AEs) will be monitored throughout the study.

